Secondary Effectiveness Objective	
 • RAP treatment effectiveness: The secondary effectiveness objective is to demonstrate the improvement in the appearance of cellulite as determined by the study participants selecting “Agree” or “Strongly Agree” as answers to the Participant Satisfaction Survey (Assessment 3): when comparing side-by-side before and after photographs.
Test Device	ZELTIQ Aesthetics, Inc. Rapid Acoustic Pulse (RAP) device.
Treatment	
Each cellulite treatment session will consist of RAP treatment [REDACTED] to bilateral thigh and/or buttock areas using the same treatment settings for both sides.
 
The participants will have three (3) separate cellulite treatment sessions. The second treatment session will occur four (4) weeks post the initial treatment. The third treatment session will occur twelve (12) weeks post the second treatment.

Control	For each cellulite treatment area, the pre-treatment photos of the thighs and/or buttocks area will serve as a control.
Study Design	Non-significant risk, single-site, prospective clinical trial.
Planned Number of Sites / Countries	One clinical trial site located in the United States.

Planned Duration of Participant Engagement	Up to seventy-two (72) weeks [REDACTED]
Planned Number of Participants/ Treatment Areas	Up to 15 participants [REDACTED] (total of two thighs and/or buttocks per participant) The clinical site (CS) will recruit up to 15 participants. This will provide a total of up to thirty treatment areas.
Primary Effectiveness Endpoint	
 Effectiveness Endpoint: An Independent Photo Review (IPR) panel will be asked to identify the 12-weeks post final treatment photographs from randomly placed side-by-side before and after photographs, for all participants who meet all the inclusion criteria and none of the exclusion criteria and complete the 12-weeks follow-up visit. The number of before and after photos correctly identified by at least 2 of 3 blinded reviewers from the IPR panel will be recorded. [REDACTED]
Primary Safety Endpoint	
 RAP treatment safety endpoint: To demonstrate safety through the absence of unexpected adverse events (UAEs) and serious adverse events (SAEs) directly attributable to the RAP device or treatments.

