Secondary Effectiveness Endpoint	
 Effectiveness Endpoint: For all participants who meet all inclusion criteria and none of the exclusion criteria and are followed up at the 12-week timepoint post final treatment, [REDACTED] he study participants select “Agree” or “Strongly Agree” to the Participant Satisfaction Survey (Assessment 3): [REDACTED]
[REDACTED]	

Inclusion Criteria	
 • Healthy candidates ages 18-50 years. • Seeking treatment of cellulite in the thigh and/or buttock areas. • Areas of moderate to severe cellulite on bilateral thigh and/or buttock using the Cellulite Dimple – At Rest Scale at Baseline with grades of 2 or 3 based on review of photos taken under the same lightening conditions planned for the trial. • Participant will not have had minimally invasive, invasive, or energy-based cellulite (liposuction, subcision, RF, laser, ESWT, cryo-lipolysis, muscle stimulation, etc.) treatments in the treatment areas in the prior 12 months. • Participant will not have used topical based cellulite treatments for prior 3 months and will not use during the trial. • Participant will not have used spray-on tanning treatments for 3 months prior to or during the term of the trial. • Participant must be able to provide written informed consent, understand and is willing to comply with all study-related procedures and follow-up visits.
Exclusion Criteria	
 • Participant is unwilling to have research photos and/or videos taken of treatment areas in the presence of or by Sponsor's research team. • Participant is unwilling to have RAP treatment provided in the presence of Sponsor's research team. • Participant is pregnant or planning to become pregnant during the duration of the study. • Participant is unwilling to commit to follow-up visits.

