Short-term (12-week) analysis was conducted in fifty-six participants who completed a full treatment of the identified treatment areas and who completed the 12-week follow up visit. Serial clinical photographs were collected before RAP treatment under standardized conditions at the baseline (0-week) visit and at the short-term (12-week) follow-up visits. Photographs were assessed by blinded independent reviewers (IPR) to correctly identify the 12-weeks post-treatment photographs from randomly placed side-by-side comparison of before and after photographs. Additionally, the IPR graded the pre-treatment and post-treatment images using the simplified 6-point Cellulite Severity Scale (CSS) [3] and improvement using the Global Aesthetic Improvement Scale (GAIS). Safety assessments included evaluation of Adverse Events (AEs) via physician examination during and after the treatment.

[figure not shown]
The short-term (12-week) results demonstrated that a single non-invasive acoustic subcision session can safely provide meaningful improvement in the appearance of cellulite in terms of depressions with minimal treatment pain and no post-treatment down time. The post-treatment photographs were correctly identified by blinded IPR from randomized pairs of pre/post-treatment photographs at a rate of 96.4%. Furthermore, the participants had a mean CSS reduction of 1.01 (a 29.5% reduction from baseline). Cellulite was graded as improved, much improved, or very much improved using the GAIS at 90.9% of treated locations. Finally, 92.9% of participants reported positive satisfaction responses. No device related unexpected or serious AEs were noted at treatment or follow-up. Overall average pain score during treatment was 2.4 (0-10 pain scale) and 0.3 immediately post-treatment.

[figure not shown]

Protocol 2021-06 Study Objectives and Endpoints

Primary Objectives	Primary Outcome Endpoints
RAP treatment effectiveness: The primary objective is to demonstrate improvement in the appearance of cellulite by blinded independent physician reviewers (IPR).	Effectiveness Endpoint: An IPR panel will be asked to identify the 12-weeks post final treatment photographs from randomly placed side-by-side before and after photographs, for all participants who meet the all inclusion criteria and none of the

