The investigational site will provide direct access to all trial-related site's source data/documents, and reports for the purpose of monitoring and auditing by ZELTIQ Aesthetics, Inc. or designee, and inspection by local and regulatory authorities (as appropriate).

The investigational site will have established standard operating procedures (SOPs) for quality management. Data will be evaluated for compliance with the protocol and accuracy in relation to source documents. The study will be conducted in accordance with procedures identified in the protocol.

The data and any research conducted will be controlled by ZELTIQ Aesthetics, Inc.

STUDY RESULTS/ANALYSIS

Sample Size Determination: Up to fifteen (15) participants will be enrolled and treated in this study. The sample size is based on clinical and practical exploratory considerations and not a formal statistical power.

Demographics and Baseline Characteristics: Demographic and baseline characteristics will include age, sex, ethnicity, race, gender identity, height, and weight, Fitzpatrick Skin Type, and Cellulite Dimple assessment of bilateral posterior thighs and/or buttocks.

Study Analysis Populations: The Full Analysis Set (FAS) will include all participants who meet all the inclusion and none of the exclusion criteria, received assigned three treatments with the device and completed the 12-week, follow-up visits per the protocol. The FAS will be treated as the primary analysis set.

Effectiveness Parameter Analysis: Descriptive statistics will be performed on the population per protocol, all participants completing the study without major protocol deviations. Descriptive statistics (i.e., mean, standard deviation, etc.) will be provided for all continuous variables, percentages and frequencies for all categorical variables collected in this study.

Summary tables will be used to present population characteristics at Baseline. For categorical parameters, the number and percentage of participants in each category will be presented. The denominator for percentage will be based on the number of participants appropriate for the purpose of analysis. For continuous parameters, descriptive statistics will include n (number of participants), mean, standard deviation, median, and range. No imputation will be used to account for missing data. No processing for outliers will be performed. Data will be presented as reported on the CRF. [REDACTED]

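### The FAS is named as primary, but the effectiveness paragraph uses a study-completer per-protocol set, so a valid 12-week photo pair can be lost to later withdrawal

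*Combined protocol and SAP*

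**What the plan says.** Study Results/Analysis, Study Analysis Populations, defines the FAS as eligible participants who "received assigned three treatments with the device and completed the 12-week, follow-up visits per the protocol". It then states: "The FAS will be treated as the primary analysis set".

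The next paragraph, Effectiveness Parameter Analysis, says: "Descriptive statistics will be performed on the population per protocol, all participants completing the study without major protocol deviations". On percentages it adds: "The denominator for percentage will be based on the number of participants appropriate for the purpose of analysis". Missing data are not imputed.

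The endpoint definitions in the Study Synopsis, repeated in the objectives table, stop at 12 weeks. The primary endpoint is assessed "for all participants who meet all the inclusion criteria and none of the exclusion criteria and complete the 12-weeks follow-up visit". The secondary endpoint covers eligible participants who "are followed up at the 12-week timepoint post final treatment".

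Visit 5 falls 12 weeks after the third treatment. Visits 6 and 7 follow at 26 and 52 weeks after it. The readable text defines neither completion of the study nor a major deviation.

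**The concern.** The effectiveness sentence adds two conditions that the FAS does not state: completing the study, and having no major deviation. Nothing readable says which set governs the 12-week endpoints, and the sentence on denominators leaves the choice open.

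The first condition matters more. The outcome is fixed once the Visit 5 photographs are taken. Withdrawal afterwards says nothing about whether that pair is valid, so it is no reason to remove the pair from a 12-week endpoint.

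The second condition is open-ended. Records Management, Protocol Deviations, has deviations adjudicated one by one while the data are being analysed, and it does not mention analysis sets. The text therefore does not ensure that per-protocol membership is settled before the results are seen.

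The primary result is a descriptive proportion from at most 15 people. Two analysts following the two paragraphs could report different percentages from the same photographs.

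**Working it through.** The readable text gives no power, threshold or withdrawal rate, and the sample size is expressly not power-based. There is no planned figure to reproduce.

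**1. The sets side by side**

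| Condition | FAS | Effectiveness sentence | Endpoint text |
|---|---|---|---|
| Eligible | yes | not stated | yes |
| Three treatments | yes | not stated | not stated |
| 12-week follow-up | yes | implied | yes |
| Study completed | no | yes | no |
| No major deviation | not stated | yes | no |

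**2. What completion means.** The protocol's own usage points to the last visit. Study Design measures duration to the last observation visit and plans up to seven visits. Reporting of Adverse Events runs to the final observation visit and follows events until they resolve or the participant completes the study. SAE Follow-up contrasts completing with withdrawing.

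**3. The exposed period.** Visit text: 52 − 12 = 40 weeks. Table 1: 64 − 24 = 40 weeks. (Table 1 puts Visit 4 at week 12, while the visit text puts it 12 weeks after the second treatment, so about week 16 if that treatment is at week 4. These need reconciling, but the 40 weeks are unaffected.)

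**4. Effect on the rate.** Assumptions: participant as unit, all 15 in the FAS, and the counts and numbers of leavers chosen for illustration.

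Removing one participant from x/15 changes the rate by
- x/14 − x/15 = x/210 if that pair was misidentified;
- (x − 1)/14 − x/15 = −(15 − x)/210 if it was correctly identified.

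The largest shift is 14/210 = 6.7 points.

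FAS 12/15 = 80.0% (exact 95% CI 51.9% to 95.7%). The probabilities below assume that leaving is unrelated to the result.

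| Two leavers | Per-protocol rate | Shift (points) | Probability |
|---|---|---|---|
| both misidentified | 12/13 = 92.3% | +12.3 | 3/105 = 2.9% |
| one misidentified | 11/13 = 84.6% | +4.6 | 36/105 = 34.3% |
| neither | 10/13 = 76.9% | −3.1 | 66/105 = 62.9% |

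With one leaver the rate is 12/14 = 85.7% (+5.7) or 11/14 = 78.6% (−1.4).

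The earlier single-session pivotal study reported 96.4% correct identification. Nearer that level, FAS 14/15 = 93.3%. Two leavers give 13/13 = 100% (+6.7, probability 2/15 = 13.3%) or 12/13 = 92.3% (−1.0, probability 86.7%). At 15/15 nothing changes.

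**5. Chance that at least one valid pair is dropped.** With an assumed late-loss rate r, this is 1 − (1 − r)^15: 53.7% at r = 5%, 79.4% at 10%, 96.5% at 20%.

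**6. Treatment area as unit.** The primary endpoint counts photos, and the Synopsis says of the 15 participants: "This will provide a total of up to thirty treatment areas". If both areas of a participant share the same result, two leavers turn 24/30 into between 20/26 = 76.9% and 24/26 = 92.3%, the same range as above.

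**The case against.** The strongest reply is that the plan already ranks the sets. The FAS is called primary, the effectiveness sentence does not call its population primary, and a per-protocol summary can sit beside an FAS analysis. The endpoint text stops at 12 weeks. The earlier pivotal study's short-term analysis likewise used participants with full treatment and the 12-week visit. The authors may simply have meant the FAS, whose definition itself asks for visits completed according to the protocol. This makes the FAS the likely intention, but it does not remove the conflict: the only readable sentence that assigns effectiveness statistics to a population assigns them to a different one.

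The size may also be small. The largest shift above is the least likely one. If 15 independent participants each had a 96.4% chance of correct identification, all would be correct with probability 0.964^15, about 58%, and late leaving would then change nothing. That is fair, though the 96.4% comes from a single-session study, and the outcome cannot be known when the rule is written.

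Text after the endpoints and at the end of the effectiveness paragraph is redacted. It may add detail, but it cannot make the two visible definitions identical.

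Two smaller points stand and affect the wording of the fix. The FAS refers to 12-week visits in the plural, and Visit 4 is also a 12-week follow-up visit. The FAS also requires three treatments, a condition the endpoint text does not state.

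**Conclusion.** The concern holds. The FAS and the population in the effectiveness sentence are different sets, and on a plain reading the latter discards valid Visit 5 photo pairs for withdrawal in the next 40 weeks. The endpoint text sides with the FAS, so the effectiveness sentence is the outlier.

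The size depends on assumed counts. With 15 participants, one exclusion moves the rate by at most 6.7 points. Two late leavers move an assumed 80.0% by between −3.1 and +12.3 points, and an assumed 93.3% by −1.0 or +6.7. The rates agree if every pair is correctly identified, or if nobody leaves late and no major deviation occurs. No direction of bias is established. The analysis is descriptive without a formal power basis, so nothing is claimed about power or type I error. This should be corrected before the photo review.

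**What to change.** - In Effectiveness Parameter Analysis, state that the primary and secondary 12-week endpoints are analysed on the FAS, regardless of withdrawal after the 12-week visit. Remove study completion as a condition for these endpoints.
- In the FAS definition, name the required visit as Visit 5, 12 weeks after the third treatment. Have the endpoint text in the Synopsis and the objectives table refer to the FAS, so that the three-treatment condition reads the same everywhere.
- Keep the per-protocol set as a named supportive analysis, with completion judged at Visit 5 and the list of major deviations fixed before the photo review.

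The cost is a few sentences, a short list of deviations and one supportive table. No extra participants, visits or photographs are needed. The reported rate may come out lower or higher than the per-protocol rate.

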THE IRB MUST BE NOTIFIED OF COMPLETION OF THIS STUDY.....	32

REFERENCES	33
TABLES.....	34
TIMELINE AND EVENTS SCHEDULE.....	34
STUDY SCALES AND ASSESSMENTS.....	35

INVESTIGATOR'S STATEMENT OF AGREEMENT

I have read the foregoing protocol and agree that it contains all necessary details for conducting the study. I will conduct the study as outlined herein and will complete the study within the time designated.

I agree to conduct this protocol in accordance with local regulations, external standards and applicable ICH and Good Clinical Practice (GCP) guidelines.

I will provide copies of the protocol, including any amendments, and all pertinent information to all individuals responsible to me who assist in the conduct of this study. I will discuss this material with them to ensure they are fully informed regarding the ZELTIQ Aesthetics, Inc. device and the conduct of the study.

I further agree to provide access to ZELTIQ Aesthetics Inc, its designees, or regulatory authorities to any source documents from which case report form information may have been generated.

I agree to maintain the confidentiality of all information received or developed in connection with this protocol.

Principal Investigator
(Print name)

Principal Investigator
(Principal Investigator's signature)

Date

[figure not shown]
CLINICAL SITE

STUDY SYNOPSIS

Purpose	The purpose of this single-site clinical study is to evaluate the safety and effectiveness of three (3) treatments sessions with the ZELTIQ Aesthetics, Inc. Rapid Acoustic Pulse (RAP) device for the improvement in the appearance of cellulite.
Primary Effectiveness Objective	
 • RAP treatment effectiveness: The primary effectiveness objective will demonstrate improvement in the appearance of cellulite as determined by correct identification of baseline vs 12-weeks post final treatment images [REDACTED] [REDACTED] by at least 2 of 3 blinded independent physician reviewers (IPR).
Primary Safety Objective	
 • RAP treatment safety: The primary safety objective is to evaluate the safety of the RAP (Rapid Acoustic Pulse) device for cellulite treatments through the monitoring of the incidence of adverse events (AEs) and adverse device effects (ADEs); serious adverse events (SAEs) and SADEs (serious adverse device effects) and pain assessments.

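### The primary objective is to demonstrate improvement, but the readable analysis gives only counts and percentages, with no visible interval or comparison with the 50% that guessing would give

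*Combined protocol and SAP*

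**What the plan says.** The Study Synopsis states the aim as follows: "The primary effectiveness objective will demonstrate improvement in the appearance of cellulite as determined by correct identification". The table under Protocol 2021-06 Study Objectives and Endpoints repeats the verb *demonstrate* for the primary effectiveness objective, in a sentence with nothing blacked out.

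The reviewers' task is to "identify the 12-weeks post final treatment photographs from randomly placed side-by-side before and after photographs". On scoring: "The number of before and after photos correctly identified by at least 2 of 3 blinded reviewers from the IPR panel will be recorded".

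Under STUDY RESULTS/ANALYSIS, Effectiveness Parameter Analysis reads "Descriptive statistics will be performed on the population per protocol", with "percentages and frequencies for all categorical variables collected in this study". The next paragraph adds the number and percentage per category and says that missing data are not imputed. Sample Size Determination caps enrolment at 15 and says: "The sample size is based on clinical and practical exploratory considerations and not a formal statistical power".

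Text is blacked out in four relevant places: inside the synopsis objective, after the endpoint sentence in the synopsis, after the same sentence in the objectives table, and at the end of the effectiveness analysis.

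**The concern.** To demonstrate something is a confirmatory claim. A count and a percentage do not say how far the result could lie from chance, and here chance is not near zero. A reviewer who sees no difference between two pictures but must choose one is right half the time. A rate of 70% to 80% reads as success, yet in a group this small it can be what guessing produces. The analysis set requires all three treatments and the 12-week visit, so the number evaluable can only be 15 or fewer. At stake is whether a reader of the final report can see at a glance that the reviewers did better than chance.

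**Working it through.** **Inputs.** Up to 15 participants and up to 30 treatment areas (Study Synopsis; Sample Size Determination). A pair counts as correct if two or more of three reviewers are right (endpoint). The earlier pivotal study had 96.4% correct (Introduction), which matches 54/56 = 0.964 if its 56 analysed participants are the denominator. The plan gives no alpha, power or dropout rate. I assume a two-sided 95% exact interval (one-sided 0.025), one result per participant, a forced choice, and 10 to 15 evaluable participants.

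**The plan's own figure.** There is no calculation to reproduce. The plan says that 15 does not come from a power calculation.

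**Chance rate under the 2-of-3 rule.** With three independent guesses, P(at least 2 correct) = 3 × 0.5² × 0.5 + 0.5³ = 0.375 + 0.125 = 0.50. If all three reviewers make the same guess it is also 0.50.

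**Chance of a given result by guessing.** P(X ≥ x) = Σ C(n,k) / 2ⁿ for k from x to n. For n = 15 the denominator is 32,768:
- 10 or more: (3003 + 1365 + 455 + 105 + 15 + 1) / 32,768 = 4944 / 32,768 = 0.151
- 11 or more: 1941 / 32,768 = 0.059
- 12 or more: 576 / 32,768 = 0.0176

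**Exact (Clopper-Pearson) 95% intervals.**

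| Correct | Rate | 95% CI | Chance of this or better by guessing | Excludes 50%? |
|---|---|---|---|---|
| 10/15 | 67% | 38.4% to 88.2% | 0.151 | no |
| 11/15 | 73% | 44.9% to 92.2% | 0.059 | no |
| 12/15 | 80% | 51.9% to 95.7% | 0.018 | yes |
| 11/14 | 79% | 49.2% to 95.3% | 0.029 | no |
| 10/13 | 77% | 46.2% to 95.0% | 0.046 | no |
| 9/12 | 75% | 42.8% to 94.5% | 0.073 | no |
| 10/12 | 83% | 51.6% to 97.9% | 0.019 | yes |
| 8/10 | 80% | 44.4% to 97.5% | 0.055 | no |
| 9/10 | 90% | 55.5% to 99.7% | 0.011 | yes |

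A one-sided 0.05 standard would let 11/14 and 10/13 through, but the cut-off at n = 15 stays at 12.

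**What a threshold on the percentage would do.** With all 15 evaluable, any threshold above 11/15 (73.3%) requires at least 12 correct and so excludes 50%. With fewer evaluable it may not: a 75% threshold is met by 11/14, 10/13 or 9/12, and an 80% threshold by 8/10, all with intervals that include 50%.

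**Unit of analysis.** The readable text does not settle whether a participant or an area is scored. Treating 30 areas as independent, 21/30 (70%, 50.6% to 85.3%) would suffice. That is too lenient if a participant's two areas tend to agree. In the extreme of full agreement, 22/30 carries only the information of 11/15: 44.9% to 92.2%, rather than 54.1% to 87.7%.

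**How often 12 or more of 15 would be reached.** P(X ≥ 12) is 99.8% if the true rate is 96.4%, 94.4% at 90%, and 64.8% at 80%.

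**The case against.** Four counter-arguments deserve weight.

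- **Redaction.** A reader might infer that the plan has no success criterion, so that a result compatible with guessing can be reported as demonstrated. The documents do not support that. The blacked-out blocks sit where a threshold, test or interval would stand. This objection stands in full and makes the point conditional.
- **A threshold may suffice.** It is also tempting to say that any hidden threshold leaves the problem untouched. That is not so: with 15 evaluable, a threshold of 75% or more already rules out 50%. It stands for full follow-up, but not for every smaller number of completers.
- **The study is openly exploratory.** Descriptive analysis fits an unpowered sample, and the synopsis uses the same verb for safety and for participant satisfaction. This stands as a reason not to impose a pass/fail rule and not to criticise the sample size. It does not remove the mismatch between verb and analysis, which rewording would also cure.
- **Readers can compute the interval themselves, and the expected effect is large.** With a count and a denominator they can, so it would be too strong to say that the report could not be interpreted. If the 96.4% rate recurs, the interval will exclude 50% almost surely. The interval matters if the effect is weaker here.

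**Conclusion.** The point holds in a limited form. In the readable text a confirmatory verb is paired with counts and percentages, with no visible interval and no comparison with the 50% chance rate. With one result per participant and all 15 evaluable, 11 or fewer correct (73% or less) is compatible with guessing at the two-sided 95% level, and 12 or more is not. With 10 evaluable, even 80% is compatible.

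This rests on a forced choice between two pictures, on the participant as the unit, and on the redacted text not already supplying an interval or an adequate criterion. It does not show that the plan lacks a criterion, that 15 participants are too few for an exploratory study, or that a misleading result is likely. It is a cheap improvement that limits what can be concluded, with small practical risk if the earlier rate recurs.

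**What to change.** Unless the redacted text already does so, add to Effectiveness Parameter Analysis that the primary correct-identification rate will be reported per participant, as a count and percentage with an exact (Clopper-Pearson) 95% confidence interval, beside the 50% expected from guessing. State the scoring unit. If areas are scored separately, do not treat a participant's two areas as independent.

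Then choose one of two courses:
- Call improvement demonstrated only if the lower limit exceeds 50%. That means at least 12 of 15 when all 15 are evaluable with one result each, at least 10 of 12, or at least 9 of 10.
- Reword the objective in the synopsis and in the objectives table so that the study estimates the rate.

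The sample size stays as it is. The cost is a couple of sentences and one table column, with no added participants. The downside of the first course is that a result such as 11/15 could not be called a demonstration.
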